# 6.3. Follow-up

# 6.3.1. Follow-up Contact

Follow-up contact will be completed at least 28 calendar days and up to 35 calendar days after the last administration of the investigational product to capture any potential adverse events (see the Time Period for Collecting AE/SAE Information section) and to confirm appropriate contraception usage (Cohort 2 only, see the Contraception section). Contact with the subject may be done via a phone call.

# 6.4. Subject Withdrawal/Early Termination

#### Withdrawal of consent:

Subjects who request to discontinue receipt of study treatment will remain in the study and must continue to be followed for protocol-specified follow-up procedures. The only exception to this is when a subject specifically withdraws consent for any further contact with him or her or persons previously authorized by the subject to provide this information. Subjects should notify the investigator in writing of the decision to withdraw consent from future follow-up, whenever possible. The withdrawal of consent should be explained in detail in the medical records by the investigator, as to whether the withdrawal is only from further receipt of investigational product or also from study procedures and/or posttreatment study follow-up, and entered on the appropriate CRF page. In the event that vital status (whether the subject is alive or dead) is being measured, publicly available information should be used to determine vital status only as appropriately directed in accordance with local law.

# Lost to follow-up:

All reasonable efforts must be made to locate subjects to determine and report their ongoing status. This includes follow-up with persons authorized by the subject as noted above. All attempts should be documented in the subject's medical records. If it is determined that the subject has died, the site will use locally permissible methods to obtain the date and cause of death. If the investigator's use of a third-party representative to assist in the follow-up portion of the study has been included in the subject's informed consent, then the investigator may use a sponsor-retained third-party representative to assist study site staff with obtaining the subject's contact information or other public vital status data necessary to complete the follow-up portion of the study. The study site staff and representative will consult publicly available sources, such as public health registries and databases, in order to obtain updated contact information. If, after all attempts, the subject remains lost to follow-up, then the last-known-alive date as determined by the investigator should be reported and documented in the subject's medical records.

Subjects may withdraw from the study at any time at their own request, or they may be withdrawn at any time at the discretion of the investigator or sponsor for safety (see also the Withdrawal From the Study Due to Adverse Events section) or behavioral reasons, or the inability of the subject to comply with the protocol-required schedule of study visits or

procedures at a given investigator site. The early termination visit applies only to subjects who are randomized and then are prematurely withdrawn from the study.

If a subject does not return for a scheduled visit, every effort should be made to contact the subject. The investigator or site staff should attempt to contact the subject twice. After 2 attempts, CRU staff may send a registered letter. If no response is received from the subject, the subject will be considered lost to follow-up. All attempts to contact the subject and information received during contact attempts must be documented in the subject's medical record. In any circumstance, every effort should be made to document subject outcome, if possible. The investigator should inquire about the reason for withdrawal, request that the subject return for a final visit, if applicable, and follow-up with the subject regarding any unresolved AEs.

It may be appropriate for the subject to return to the clinic for final safety assessments to be scheduled as early as practically feasible following the decision to withdraw from the study. Subjects should be questioned regarding their reason for withdrawal. At the early-withdrawal visit, every effort must be made to complete the following assessments:

#### Cohort 1

- Review and record concomitant medications.
- Assess the skin irritation response of the patch sites.
- Conduct physical examination
- Assess symptoms by spontaneous reporting of AEs and by asking the subjects to respond to a nonleading question such as "How do you feel?" If AEs/SAEs occur at a patch site, the patch site location must be recorded.

#### Cohort 2

- Review and record concomitant medications.
- Collect 12-lead ECG measurements prior to insertion of the IV catheter.
- Collect supine BP and PR prior to insertion of the IV catheter.
- Obtain blood and urine samples for safety laboratory tests.
- Collect a blood sample for PK analysis.
- Conduct physical examination
- Assess symptoms by spontaneous reporting of AEs and by asking the subjects to respond to a nonleading question such as "How do you feel?"

Lack of completion of all or any of the withdrawal/early termination procedures will not be viewed as protocol deviations so long as the subject's safety was preserved.

If the subject withdraws from the study and also withdraws consent for disclosure of future information, no further evaluations should be performed and no additional data should be collected. The sponsor may retain and continue to use any data collected before such withdrawal of consent.

Subjects who withdraw from the study may be replaced at the discretion of the investigator upon consultation with the sponsor.

#### 7. ASSESSMENTS

Every effort should be made to ensure that protocol-required tests and procedures are completed as described. However, it is anticipated that from time to time there may be circumstances outside the control of the investigator that may make it unfeasible to perform the test. In these cases, the investigator must take all steps necessary to ensure the safety and well-being of the subject. When a protocol-required test cannot be performed, the investigator will document the reason for the missed test and any corrective and preventive actions that he or she has taken to ensure that required processes are adhered to as soon as possible. The study team must be informed of these incidents in a timely manner.

For samples being collected and shipped, detailed collection, processing, storage, and shipment instructions and contact information will be provided to the investigator site prior to initiation of the study.

#### **7.1. Safety**

# 7.1.1. Laboratory Tests

The following safety laboratory tests will be performed at times defined in the STUDY PROCEDURES section of this protocol. Additional laboratory results may be reported on these samples as a result of the method of analysis or the type of analyzer used by the clinical laboratory; or as derived from calculated values. These additional tests would not require additional collection of blood. Unscheduled clinical laboratory measurements may be obtained at any time during the study to assess any perceived safety concerns.

The clinical laboratory test parameters that will be reviewed for safety evaluation are presented in Table 3.

Table 3. Safety Laboratory Tests			
Hematology	Chemistry	Urinalysis	Other
Hemoglobin	BUN/urea and creatinine	pH	FSH b
Hematocrit	Glucose (fasting)	Glucose (qual)	Urine drug screening
RBC count	Calcium	Protein (qual)	β-hCG c
MCV	Sodium	Blood (qual)	HIV
MCH	Potassium	Ketones	HepBsAg
MCHC	Chloride	Nitrites	HepBcAb
Platelet count	AST, ALT	Leukocyte esterase	HCVAb,
WBC count	Total bilirubin	Urobilinogen	Syphilis
Total neutrophils (%)	Alkaline phosphatase	Urine bilirubin	
Eosinophils (%)	Uric acid	Microscopy a	
Monocytes (%)	Albumin		
Basophils (%)	Total protein		
Lymphocytes (%)	-		
	Additional Tests, as		
	applicable (Needed for		
	Hy's Law)		
	AST, ALT (repeat)		
	Total bilirubin (repeat)		
	Albumin (repeat)		
	Alkaline phosphatase		
	(repeat)		
	Direct bilirubin		
	Indirect bilirubin		
	Creatine kinase		
	GGT		
	PT/INR		
	Total bile acids		
	Acetaminophen drug		
	and/or protein adduct		
	levels		

Abbreviations: ALT=alanine transaminase; AST=aspartate transaminase; β-hCG=beta human chorionic gonadotropin; BUN= blood urea nitrogen; FSH=follicle-stimulating hormone; GGT=gamma-glutamyl transferase; HIV=human immunodeficiency virus; HepBsAg=hepatitis B surface antigen; HepBcAb=hepatitis B core antibody; HCVAb=hepatitis C antibody; INR= international normalized ratio; MCH=mean corpuscular hemoglobin; MCHC=mean corpuscular hemoglobin concentration; MCV=mean corpuscular volume; PT=prothrombin time; RBC=red blood cell; WBC = white blood Cell. a Only if urine dipstick is positive for blood, protein, nitrites or leukocyte esterase.

- b Any female subject who has been amenorrheic for at least 12 consecutive months.
- c Urine β-hCG for female subjects of childbearing potential.
  - The minimum requirement for drug screening includes cocaine, tetrahydrocannabinol (THC), opiates/opioids, benzodiazepines, and amphetamines.
  - Subjects may undergo random urine drug testing at the discretion of the investigator. Drug testing conducted prior to dosing must be negative for subjects to receive investigational product.

# 7.1.2. Pregnancy Testing (Cohort 2)

For female subjects of childbearing potential, a urine pregnancy test, with sensitivity of at least 25 mIU/mL, will be performed at screening, and at admission on Day -1, if applicable.

A negative pregnancy test result is required before the subject may receive the investigational product. Pregnancy tests will also be done whenever 1 menstrual cycle is missed during the active treatment period (or when potential pregnancy is otherwise suspected). Pregnancy tests may also be repeated if requested by institutional review boards (IRBs)/ECs or if required by local regulations.

In the case of a positive confirmed pregnancy, the subject will be withdrawn from application of investigational product and from the study.

# 7.1.3. Physical Examinations

Physical examinations may be conducted by a physician, and especially skin examination may be conducted by a dermatologist. A physical examination will include head, ears, eyes, nose, mouth, skin, heart and lung examinations, lymph nodes, gastrointestinal, musculoskeletal, neurological systems, general appearance, the respiratory and cardiovascular systems, and subject-reported symptoms.

For measuring weight, a scale with appropriate range and resolution is used and must be placed on a stable, flat surface. Subjects must remove shoes, bulky layers of clothing, and jackets so that only light clothing remains. They must also remove the contents of their pockets and remain still during measurement of weight.

#### 7.1.4. Blood Pressure and Pulse Rate

BP and PR will be measured at times specified in the STUDY PROCEDURES section of this protocol. Additional collection times, or changes to collection times, of BP and PR will be permitted, as necessary, to ensure appropriate collection of safety data.

Supine BP will be measured with the subject's arm supported at the level of the heart, and recorded to the nearest mm Hg after approximately 5 minutes of rest. The same arm (preferably the dominant arm) will be used throughout the study. Subjects should be instructed not to speak during measurements.

The same properly sized and calibrated BP cuff will be used to measure BP each time. The use of an automated device for measuring BP and PR is acceptable; however, when done manually, PR will be measured in the brachial/radial artery for at least 30 seconds. When the timing of these measurements coincides with a blood collection, BP and PR should be obtained prior to the nominal time of the blood collection.

#### 7.1.5. Electrocardiogram

A single 12-lead ECGs should be collected at times specified in the STUDY PROCEDURES section of this protocol.

All scheduled ECGs should be performed after the subject has rested quietly for at least 5 minutes in a supine position.

For Cohort 2, to ensure safety of the subjects, a qualified individual at the investigator site will make comparisons to baseline measurements. If the QTc interval is increased by  $\geq$ 45 msec from the baseline, or an absolute QTc value is  $\geq$ 500 msec for any scheduled ECG, then 2 additional ECGs will be collected, approximately 2 to 4 minutes apart, to confirm the original measurement. If either of the QTc values from these repeated ECGs remains above the threshold value (ie, is  $\geq$ 45 msec from the baseline, or is  $\geq$ 500 msec), then a single ECG must be repeated at least hourly until QTc values from 2 successive ECGs fall below the threshold value that triggered the repeat measurement.

If QTc values remain  $\geq$ 500 msec (or  $\geq$ 45 msec from the baseline) for greater than 4 hours (or sooner, at the discretion of the investigator), or QTc intervals get progressively longer, the subject should undergo continuous ECG monitoring. A cardiologist should be consulted if QTc intervals do not return to less than 500 msec (or to  $\leq$ 45 msec above the baseline) after 8 hours of monitoring (or sooner, at the discretion of the investigator).

In some cases, it may be appropriate to repeat abnormal ECGs to rule out improper lead placement as contributing to the ECG abnormality. It is important that leads are placed in the same positions each time in order to achieve precise ECG recordings. If a machine-read QTc value is prolonged, as defined above, repeat measurements may not be necessary if a qualified medical provider's interpretation determines that the QTc values are in the acceptable range.

#### 7.1.6. Skin Irritation Assessment (Cohort 1)

Skin irritation assessment of the patch sites will be conducted on Day 3 (approximately 30 minutes after removal of the patches) and Day 4 (approximately 24 hours after removal of the patches) by a blinded observer who is a dermatologist. The following grade and score will be used to evaluate the response observed at the time of examination 20,21,22:

Table 4.	Skin I	rritation	Assessment	Grades and	Scores

Definition	Grade	Score
No reaction	=	0
Mild erythema	±	0.5
Erythema	+	1
Erythema + edema, papula	++	2
Erythema + edema + papula + small water blister	+++	3
Large water blister	++++	4

Expected reactions in the patch area (ie, irritation reactions outlined in Table 4 above) will not be recorded as AEs during the study. Unexpected reactions (eg, rash, hives) will be recorded as AEs.

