### Final Protocol Amendment 1, 14 July 2017

- a. Day relative to start of study treatment (Day 1).
- b. Follow-up contact will be completed on Day 29 (28+7 calendar days after the application of the investigational product patches on Day 1) to capture any potential adverse events.
- c. Subjects will be admitted to the Clinical Research Unit (CRU) on Day -1.
- d. Subjects will discharge from CRU on Day 4 after completion of all assessment on Day 4.
- e. Day -1 clinical labs do not have to be repeated if clinical labs are completed within 7 days prior to Day -1.
- f. Vital signs (pulse rate and blood pressure) taken supine position after subject has been calmly lying for 5 minutes.
- g. Single ECG will be collected.
- h. Day -1 urine drug testing does not have to be repeated if urine drug testing is completed within 7 days prior to Day -1.
- i. Day 1 patches remains in place through Day 3.
- j. Skin irritation assessment of the patch sites will be conducted on Day 3 (approximately 30 minutes after removal of the patches) and Day 4 (approximately 24 hours after removal of the patches).
- k. All medications and non-medication therapies used within 28 days prior to the planned first dose.
- 1. If AEs/SAEs occur at a patch site, the patch site location must be recorded.

Day a	−28 to −2	-1	1	2	3	4	5	6	7	8/ET	9	36 (+7 days)
•	Screening											FU Contact b (EOS)
Informed Consent	X											
CRU confinement		X c	$\rightarrow$	$\rightarrow$	$\rightarrow$	$\rightarrow$	$\rightarrow$	$\rightarrow$	$\rightarrow$	$\rightarrow$	$X^{d}$	
Inclusion/Exclusion Criteria	X	X	X									
Medical History	X	X										
Confirmation of Diagnosis of AD	X											
Physical Examination	X	X								Xe	X	
Physical Examination (skin examination)	X		X								X	
Assess ISGA	X		X									
Record treatable AD areas			X									
Calculate and Record Treatable %BSA g	X		X									
Safety laboratory	X	X								X		
Demographics	X											
Height and Weight	X		X h									
Vital Signs i	X		X							X		
ECG	$\mathbf{X}^{\mathrm{j}}$		$\mathbf{X}^{\mathbf{j}}$							X j		
Urine Pregnancy test	X	X										
Contraception check	X	X									X	X
FSH k	X											
HIV, HepBsAg, HepBcAb, HCVAb and syphilis testing	X											
Urine drug testing	X	X										
AM Dosing: Weigh dose and apply			X	X	X	X	X	X	X	X		
PM Dosing: Weigh dose and apply				X	X	X	X	X	X			

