### 3. STUDY DESIGN

# 3.1. Study Overview

This is a Phase 1, single-center, randomized, vehicle-controlled, parallel-cohort study of crisaborole ointment 2% to evaluate the skin irritation potential in adult Japanese healthy subjects in Cohort 1, and to evaluate the safety, tolerability and PK in adult Japanese subjects with mild to moderate AD in Cohort 2. Both cohorts will be run in parallel and completion of Cohort 1 is not required to make a decision to proceed with Cohort 2.

	Cohort	N	Investigational products
Cohort 1	Skin irritation cohort in	20	Crisaborole ointment 2% and vehicle
	healthy subjects		
Cohort 2	Safety, tolerability and PK	12	Crisaborole ointment 2% (n=10)
	cohort in subjects with mild		Vehicle (n=2)
	to moderate AD		, ,

# Cohort 1

This is a randomized, observer and subject-blind, vehicle-controlled cohort, of the investigational products (crisaborole ointment 2% and vehicle) under occlusive patch conditions to evaluate the skin irritation potential and safety in Japanese healthy male subjects aged 20 to 55 years, inclusive. Approximately 20 subjects will be enrolled into the cohort. All subjects will have skin area fields designated for the investigational products patches at two randomly assigned, adjacent sites, for the purpose of determining irritation potential.

The investigational products will be applied to one side of the infrascapular area of the back. Evaluation of dermal reactions at the application sites will be assessed clinically using a visual scale that rates the degree of erythema, edema, and other signs of skin irritation (see Section 7.1.6).

The investigational products will be applied topically once on Day 1 and remain under occlusion for 48 hours. The skin irritancy will be evaluated approximately 30 minutes after removal of the patches (Day 3, around 48 hours after the investigational products patches application) and 24 hours after removal of the patches (Day 4, approximately 72 hours after the investigational products patches application). A follow-up telephone call (end of study) will be made by study site staff to the subjects on Day 29 (+7 days) to assess AEs.

All applications of the investigational product will be conducted by the study site staff.

The observer and subjects will be blinded to minimize evaluation bias for skin irritation.

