## 6.2.1.1. Day -1

Subjects will be admitted to the CRU at least the day prior to Day 1 dosing. The following procedures will be completed following admission to the CRU:

- Review inclusion and exclusion criteria:
- Obtain blood and urine samples for safety laboratory tests. The results must have no clinically significant findings, as judged by the investigator, in order for a subject to be given investigational product on Day 1. Do not have to be repeated if clinical labs are completed within 7 days prior to Day –1;
- Collect urine for drug testing. Do not have to be repeated if urine drug testing is completed within 7 days prior to Day -1;
- Assess baseline symptoms/AEs;
- Review changes in the subject's medical history, including medication history since screening;
- Conduct physical examination.

# 6.2.1.2. Day 1

**Prior to dosing**, the following procedures will be completed:

- Review inclusion and exclusion criteria:
- Assess baseline symptoms /AEs;

- Review and record prior medications;
- Assess the application field;
- After all predose procedures have been completed, apply the investigational product patches (see the Administration section).

**After application of the investigational product patches**, the following procedures will be completed:

• Assess symptoms by spontaneous reporting of AEs and by asking the subjects to respond to a nonleading question such as "How do you feel?" If AEs/SAEs occur at a patch site, the patch site location must be recorded.

# 6.2.1.3. Day 2

The following procedures will be completed:

- Review and record concomitant medications;
- Assess symptoms by spontaneous reporting of AEs and by asking the subjects to respond to a nonleading question such as "How do you feel?" If AEs/SAEs occur at a patch site, the patch site location must be recorded;
- Confirm patches remain in place appropriately.

# 6.2.1.4. Day 3

The following procedures will be completed:

- Review and record concomitant medications;
- Remove the investigational product patches (48 hours post application on Day 1);
- Assess the skin irritation response of the patch sites by a blinded observer approximately 30 minutes after removal of the patches;
- Assess symptoms by spontaneous reporting of AEs and by asking the subjects to respond to a nonleading question such as "How do you feel?" If AEs/SAEs occur at a patch site, the patch site location must be recorded.

## 6.2.1.5. Day 4

The following procedures will be completed:

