# 8.1.4. Time Period for Collecting AE/SAE Information

The time period for actively eliciting and collecting AEs and SAEs ("active collection period") for each subject begins from the time the subject provides informed consent, which is obtained before the subject's participation in the study (ie, before undergoing any study-related procedure and/or receiving investigational product), through and including a minimum of 28 calendar days after the last administration of the investigational product.

For subjects who are screen failures, the active collection period ends when screen failure status is determined

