# 8.1.4.1. Reporting SAEs to Pfizer Safety

All SAEs occurring in a subject during the active collection period are reported to Pfizer Safety on the CT SAE Report Form.

SAEs occurring in a subject after the active collection period has ended are reported to Pfizer Safety if the investigator becomes aware of them; at a minimum, all SAEs that the investigator believes have at least a reasonable possibility of being related to investigational product must be reported to Pfizer Safety.

Follow up by the investigator continues throughout and after the active collection period and until the event or its sequelae resolve or stabilize at a level acceptable to the investigator, and Pfizer concurs with that assessment.

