# 9.5.2. Skin Irritation Analysis (Cohort 1)

For each subject, the maximum irritation score of the skin irritation assessment through all visits (ie, Day 3 and Day 4) will be calculated.

The primary endpoint for the skin irritation assessment will be the skin irritation index. For each investigational product, the skin irritation index will be calculated as the sum of the individual maximum irritation scores divided by the number of evaluable subjects who have the skin irritation assessment and multiplied by  $100.^{23}$  The calculated skin irritation index will range from 0 to 400. As show in Table 5, for example, when the skin irritation index is equal to or smaller than 5, the investigational product will be categorized as 'Safe'.

Table 5. Safety Criteria of Skin irritation index

Skin irritation inde	x a Category
0≤ - ≤5	Safe
5< - ≤15	Acceptable
15< - ≤30	Improvable
30< - ≤400	Risky

a: Skin irritation index = (Sum of higher scores in two assessments / number of evaluable subjects) × 100

For the maximum irritation score, the frequency (number and %) of individual maximum irritation scores will be presented for each investigational product. The descriptive statistics [number, mean, standard deviation (SD), median, minimum and maximum] of the maximum irritation score will also be calculated for each investigational product.

For the irritation score, the frequency (number and %) of individual irritation scores will be presented for each investigational product at each visit. The descriptive statistics (number, mean, SD, median, minimum and maximum) of the irritation score will also be calculated for each investigational product at each visit.

Individual irritation scores will be displayed in a data listing for all subjects.

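### The Cohort 1 AE exemption for Table 4 patch-site reactions has no onset-day limit, so a non-serious reaction arising or worsening after the Day 4 assessment can count in neither the skin irritation index nor the AE endpoint

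*Protocol*

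**What the plan says.** **AE exemption.** Protocol Section 7.1.6 says of the Cohort 1 patch sites: "Expected reactions in the patch area (ie, irritation reactions outlined in Table 4 above) will not be recorded as AEs during the study". It continues: "Unexpected reactions (eg, rash, hives) will be recorded as AEs". Both sentences sort reactions by type. Neither mentions day of onset or seriousness. Table 4 runs from no reaction (score 0) to large water blister (score 4).

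**Scoring.** Sections 3.1 and 7.1.6 schedule assessments on Day 3 and Day 4. Section 9.5.2 takes each subject's maximum score "through all visits (ie, Day 3 and Day 4) will be calculated", and SAP Section 6.3.1 says the same. That maximum feeds the skin irritation index, the Cohort 1 primary endpoint.

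**AE collection.** AEs are the Cohort 1 secondary endpoint, and SAP Section 6.2.1 adds a by-treatment summary of application-area AEs. Section 8.1.4 runs active collection "through and including a minimum of 28 calendar days after the last administration of the investigational product". Section 3.1 places the end of study at a contact on Day 29: "follow-up telephone call (end of study) will be made by study site staff to the subjects on Day 29 (+7 days"). Footnote b of the Cohort 1 schedule gives its timing and purpose: "28+7 calendar days after the application of the investigational product patches on Day 1) to capture any potential adverse events".

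**Patch-site events and SAEs.** The Day 1 to Day 4 procedures (Sections 6.2.1.2 to 6.2.1.5) say: "If AEs/SAEs occur at a patch site, the patch site location must be recorded". Section 8.1.4.1 says: "All SAEs occurring in a subject during the active collection period are reported to Pfizer Safety on the CT SAE Report Form".

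**The concern.** The natural reason for the exemption is to avoid counting the same reaction in both the index and the AE table. That reason holds only while reactions are being scored. After the Day 4 assessment there is no further scheduled score, but the exemption continues in the words of Section 7.1.6 until the study ends.

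What is at stake is the secondary endpoint, and in particular the by-treatment summary of application-area AEs. A late non-serious patch-site reaction could be left out altogether, or recorded by one reader and omitted by another. The end-of-study call is made to find AEs, yet a reaction it reveals at the treated skin may not be recordable.

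**Working it through.** **1. The plan's own figures.** Index = 100 × (sum of individual maximum scores) / (evaluable subjects). With 20 subjects all scoring 0, 100 × 0/20 = 0. With all scoring 4, 100 × 80/20 = 400. This reproduces the stated range of 0 to 400. For the follow-up contact, Day 29 − Day 1 = 28 days and Day 36 − Day 1 = 35 days, which matches footnote b.

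**2. Period with AE collection but no scheduled score.** Day 29 − Day 4 = 25 days. With contact at the end of the window, Day 36 − Day 4 = 32 days. As shares of follow-up after application, 25/28 = 89% and 32/35 = 91%. These are calendar lengths, not risks.

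**3. Where each kind of reaction is counted under the literal text.**

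| Patch-site reaction | Index | AE endpoint |
|---|---|---|
| Table 4 type, scored on Day 3 or Day 4 | Yes | No, by design |
| Table 4 type, first appears after the Day 4 assessment, non-serious | No | No |
| Scored on Day 3 or Day 4, worsens later, non-serious | Earlier score only | Worsening not recorded |
| Seen only at an early-termination assessment on another day | Not under Section 9.5.2 as worded | No |
| Judged unexpected, for example rash or hives, after Day 4 | No | Yes |
| Serious | Only if scored on Day 3 or Day 4 | Section 8 requires it; Section 7.1.6 is silent |

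The second and third rows are the gap. The fourth arises because Section 6.4 calls for a skin irritation assessment at early withdrawal, whenever that occurs. The schedule labels the last column Day 4/ET, but the maximum score is defined on Day 3 and Day 4. The visit windows in SAP Appendix 1 apply to Cohort 2 only.

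**4. Overlap between exempt and recordable reactions.** Table 4 has 5 non-zero grades. Erythema is part of 4 of them and papules of 2. A late red or papular patch site can therefore be described as a Table 4 reaction (exempt) or as rash (an AE).

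**5. Who decides.** On Day 3 and Day 4 the scorer is a blinded dermatologist. The closing call is made by site staff. Under Section 5.2 all Cohort 1 site staff except the observer are unblinded, although access to the allocation by staff who do not handle the patches is to be kept to a minimum. The choice of term may therefore be made by someone who knows which site received which product.

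**6. Weight of one reaction.** Each subject receives both products, so with 20 treated subjects one subject is 1/20 = 5% of a product's AE table.

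**The case against.** The strongest reply is context. The exemption sits in a section about the Day 3 and Day 4 examinations, and Table 4 is introduced as grading what is seen at examination. On that reading, only reactions graded there are exempt. The reading is possible, but the operative sentence covers the whole study, and nothing in Section 8 or the SAP narrows it.

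Second, there are other routes by which a late reaction may come to light:

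- AEs are elicited with non-leading questions (Section 8.1.2).
- Unplanned visits are allowed (Schedule of Activities).
- Clinically significant abnormalities at discharge are followed up (Section 6.2.1.5).
- Symptoms that are not in Table 4, such as itch or pain, are not exempt.

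This stands in part. These routes may document a late reaction, but they do not make a Table 4 type reaction recordable as an AE.

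Third, few late reactions should be expected. In the earlier patch study (Section 1.3.3.2), 21 days of daily patches in 40 subjects gave very minimal irritation, and none of 238 subjects showed sensitization. This stands and limits the weight of the point. It is not full reassurance, because Section 1.4.1 describes those subjects as Western and cites conflicting literature on racial differences in irritant response as a reason for this cohort.

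Fourth, the sponsor's data standards or CRF instructions may already set the boundary. They are not in the documents, so this cannot be checked.

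**Conclusion.** The point holds as a defect of wording with a limited effect on the safety endpoint. Followed literally, Section 7.1.6 lets a non-serious Table 4 type reaction that starts or worsens after the Day 4 assessment count in neither Cohort 1 endpoint, or makes its recording depend on the word chosen. The weight is 5% of a product's AE table per subject, assuming 20 treated subjects. The table is descriptive and no hypothesis is tested (SAP Section 5.1). The number of such reactions is unknown. The text should be corrected, but the cohort's main conclusion does not depend on it.

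A reader might infer three stronger claims that the documents do not support:

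- *The primary result is biased.* The index is defined on Day 3 and Day 4 scores, so a later reaction leaves it and its safety category unchanged. Converting late reactions into index points would measure a different endpoint.
- *Serious patch-site reactions escape reporting.* Sections 8.1, 8.1.4.1 and 8.4.1 require all SAEs to be reported, and the Cohort 1 procedures foresee SAEs at a patch site. Section 7.1.6 does not say how it relates to these rules, which calls for a clarifying clause. It is not a direct contradiction.
- *Every late reaction is lost.* Anything judged unexpected is still an AE, so loss is possible but not certain.

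**What to change.** Reword Section 7.1.6 as follows:

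- Limit the exemption to reactions whose score at the Day 3 or Day 4 assessment enters the skin irritation index.
- Record as AEs, with patch location, Table 4 type reactions that first appear or are reported as worse after the Day 4 assessment.
- Do the same for reactions seen only at an early-termination assessment that does not enter the index. Exempting every early-termination score would recreate the gap.
- State that Section 7.1.6 does not limit SAE recording and reporting under Section 8.

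The cost is one protocol paragraph and one CRF instruction, with no added visits, staff or samples. There are two small downsides. A reaction scored on Day 3 or Day 4 that later worsens, or that is serious, will appear in both the index and the AE table, which a table footnote can explain. Worsening reported by telephone will not carry a Table 4 grade, so some judgement remains in that report.
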